10.1.2 MANDATORY Tumor Tissue Submissions
Representative formalin-fixed paraffin-embedded (FFPE) tumor tissue blocks:

A. Baseline Diagnostic Tumor Tissue

Submit the following:

- all available tumor tissue blocks, OR
- two (2) representative unstained FFPE slides per block, OR
- one (1) representative H&E slide and one (1) representative unstained slide per block.

NOTE: If the patient has consented to undergo a research biopsy to obtain tumor tissue for laboratory research studies, material captured prior to start of treatment may be submitted as outlined below in lieu of archived FFPE. If a research biopsy from consenting patients is submitted for the mandatory baseline diagnostic submission, an FFPE block must be submitted.

B. Post Neo-adjuvant Surgical Resection Tumor Tissue

Submit the following from the surgically resected specimen:

- all available tumor tissue blocks, OR
- two (2) representative unstained FFPE slides per block, OR
- one (1) representative H&E slide and one (1) representative unstained slide per block.

NOTE: A three-dimensional macroscopic measurement of the largest grossly positive identified lymph node should be provided in the gross description accompanying the specimen. If the largest grossly positive lymph node measures < 5 cm in greatest dimension, then each grossly positive lymph node should be submitted entirely at 2 mm serially sectioned intervals. For any grossly positive lymph node measuring > 5 cm in greatest dimension, representative sections of the largest lymph nodes may be utilized to avoid oversampling. Following serial sectioning of each lymph node, for those nodes > 5 cm, sections representing a complete cross section of the entire surface area should be submitted per 1 cm of each grossly positive lymph node. Sections submitted should include grossly obvious tumor. All grossly positive lymph nodes < 5 cm in specimens (where the largest node(s) exceeds 5 cm) should be submitted entirely.

Rev Add2

10.1.3 Tumor Tissue Submissions per Patient Consent

10.1.3.1 Additional Baseline Archive and Surgical FFPE Tumor Tissue

If only slides are submitted for the mandatory central diagnostic review, additional tumor tissue is requested to be submitted for laboratory research studies from patients who answer "Yes" to "*My leftover tissue samples and related information may be kept in a Biobank for use in future health research*" or "*I agree to have my tissue samples collected from procedures performed as part of my standard of care and I agree that my tissue samples and related health information may be used for the laboratory research studies described above.*"

- Twenty (20) 5 μ m and five (5) 4 μ m unstained, positively charged, air-dried plus slides from the thickest part of the tumor
- Also requested: One (1) or more core punches (minimum of 4mm diameter). If core punch tool is unavailable, request core punch kit from the ECOG-ACRIN CBPF [contact]. Adequately label every slide and core submitted, with slides numbered sequentially in the order cut.

10.1.3.2 Research Biopsies

From patients who consent "Yes" to "*I agree to have one or two research biopsies to collect tissue for known laboratory research studies.*"

Tumor tissue **blocks** from biopsies performed to obtain research specimens are to be submitted within one (1) month of the procedure. Biopsies are done only if they can be performed at minimal risk (no more than 2% risk of serious complication requiring hospitalization) and are requested at:

- Baseline, following step 1 registration prior to treatment. If a baseline biopsy is performed after study registration, the baseline FLT-PET/ CT scan should be completed prior to biopsy (can be done same day). This biopsy is requested only if there is no material available from a prior procedure performed within two (2) months of imaging.
- Two (2) weeks (+/- 1 week) post treatment.

Tumor tissue specimens will be obtained from the target lymph node metastasis, with or without image guidance. Types of biopsies are to include: 3-4 (1-2 cm in length), 14-16 or 18-gauge core biopsies, or small incisional biopsies (tumor biopsy at least 4-5 mm in diameter) such that the smallest dimension of the residual tumor after initial biopsy

would be at least 1cm. It is suggested that core biopsies be submitted separately into individual tissue blocks.

NOTE: Reimbursement guidelines for research biopsies are outlined in [Appendix XI](#).

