3.1.2.4 Stage IIID

T4b N3b/c M0 (if 3c: at least 1 clinically evident node)
Yes _____ No _____

_____ 3.1.3 Patient must have measurable disease on baseline imaging scans, obtained within 4 weeks prior to registration as defined by RECIST in Section [6.1.3](#) and by the following criteria.

_____ 3.1.3.1 All melanoma tumors must be completely resectable as determined by a surgical oncologist or experienced melanoma surgeon prior to registration.

_____ 3.1.3.1.1 Extensive satellitosis or extensive in transit metastases are not considered completely resectable.

_____ 3.1.4 Patient must have BRAF V600 mutation positive based on report from CLIA certified laboratory.

_____ 3.1.5 Patient must be medically fit to undergo surgery.

_____ 3.1.6 Patient must have adequate bone marrow, organ function and laboratory parameters (labs must be obtained \leq 14 days prior to registration) as defined below:

_____ 3.1.6.1 ANC $\geq 1.5 \times 10^9/L$
ANC: _____ Date of Test: _____

_____ 3.1.6.2 Hemoglobin $\geq 8 \text{ g/dL}$ without transfusion
Hemoglobin: _____ Date of Test: _____

_____ 3.1.6.3 Platelets $\geq 100 \times 10^9/L$ without transfusion
Platelets: _____ Date of Test: _____

_____ 3.1.6.4 AST and ALT $\leq 2.0 \times$ Institutional ULN;
AST: _____ Institutional ULN: _____
Date of Test: _____
ALT: _____ Institutional ULN: _____
Date of Test: _____

_____ 3.1.6.5 Total bilirubin $\leq 1.5 \times$ Institutional ULN and $< 2 \text{ mg/dL}$; OR total bilirubin $> 1.5 \times$ Institutional ULN with indirect bilirubin $< 1.5 \times$ Institutional ULN
Total Bilirubin: _____ Institutional ULN: _____
Indirect Bilirubin: _____ Institutional ULN: _____
Date of Test: _____

_____ 3.1.6.6 Serum creatinine $\leq 1.5 \times$ Institutional ULN, or calculated creatinine clearance $> 50 \text{ mL/min}$ by Cockroft-Gault formula
Creatinine: _____ Institutional ULN: _____
Date of Test: _____

Creatinine Clearance: _____ Date of Test: _____

_____ 3.1.6.7 PT, INR, and PTT $\leq 1.5 \times$ Institutional ULN

PT: _____ Institutional ULN: _____

Date of Test: _____

INR: _____ Institutional ULN: _____

Date of Test: _____

PTT: _____ Institutional ULN: _____

Date of Test: _____

- _____ 3.1.7 Patient must have an ECOG Performance status 0-1.
- _____ 3.1.8 Patient must not have any prior treatment with BRAFi or MEKi.
- _____ 3.1.9 Patient must not have any evidence of distant metastases.
- _____ 3.1.10 Patient must be able to take oral medications.

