6.1.5.2 RECIST Evaluation of Target Lesions

Complete Response (CR)

Disappearance of all target lesions. Any pathological lymph nodes (whether target or non-target) must have reduction in short axis to < 10 mm.

Partial Response (PR)

At least a 30% decrease in the sum of the diameters of target lesions, taking as reference the baseline sum diameters.

Progressive Disease (PD)

At least a 20% increase in the sum of the diameters of target lesions, taking as reference the smallest sum on study (this includes the baseline sum if that is the smallest on study). In addition to the relative increase of 20%, the sum must also demonstrate an absolute increase of at least 5 mm.

NOTE: The appearance of one or more new lesions is also considered progression, See Section [6.1.5.4](#).

Stable Disease (SD)

Neither sufficient shrinkage to qualify for PR nor sufficient increase to qualify for PD, taking as reference the smallest sum diameters while on study.

NOTE: A change of 20% or more that does not increase the sum of the diameters by 5 mm or more is coded as stable disease.

To be assigned a status of stable disease, measurements must have met the stable disease criteria at least once.

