6.1.5.5 Evaluation of Best Overall Response

The best overall response is the best response recorded from the start of the neoadjuvant treatment until surgery or disease progression/recurrence or non-protocol therapy (taking as reference for progressive disease the smallest measurements recorded since the treatment started).

Best response will be collected at one time point:

- After 8 weeks of neoadjuvant therapy (best response to oral treatment)

RECIST response with Measurable Disease (i.e., Target Disease)

Target Lesions	Non-Target Lesions	New Lesions*	Best Overall Response	Remarks
CR	CR	No	CR	
CR	Non-CR/Non-PD***	No	PR	
CR	Not evaluated	No	PR	
PR	Non-PD***/not evaluated	No	PR	
SD	Non-PD***/not evaluated	No	SD	
PD	Any	Yes or No	PD	No prior SD, PR or CR
Any	PD**	Yes or No	PD***	
Any	Any	Yes	PD	

* See RECIST 1.1 manuscript for further details on what is evidence of a new lesion.

** In exceptional circumstances, unequivocal progression in non-target lesions may be accepted as disease progression.

*** PD in non-target lesions should not normally trump target lesion status. It must be representative of overall disease status change, not a single lesion increase. Please refer to the Evaluation of Non-Target Lesions – Progressive Disease section for further explanation.

NOTE: Patients with a global deterioration of health status requiring discontinuation of treatment without objective evidence of disease progression at that time should be reported as "*symptomatic deterioration*." Every effort should be made to document the objective progression even after discontinuation of treatment.

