NOTE: A three-dimensional macroscopic measurement of the largest grossly positive identified lymph node should be provided in the gross description accompanying the specimen. If the largest grossly positive lymph node measures < 5 cm in greatest dimension, then each grossly positive lymph node should be submitted entirely at 2 mm serially sectioned intervals. For any grossly positive lymph node measuring > 5 cm in greatest dimension, representative sections of the largest lymph nodes may be utilized to avoid oversampling. Following serial sectioning of each lymph node, for those nodes > 5 cm, sections representing a complete cross section of the entire surface area should be submitted per 1 cm of each grossly positive lymph node. Sections submitted should include grossly obvious tumor. All grossly positive lymph nodes < 5 cm in specimens (where the largest node(s) exceeds 5 cm) should be submitted entirely.

From Consenting Patients:

Research Biopsies

- Representative formalin-fixed paraffin-embedded (FFPE) tumor tissue blocks from baseline following step 1 registration (prior to treatment) and two weeks post treatment biopsy.

NOTE: This baseline research biopsy is requested only if there is no material available from a prior procedure performed within two (2) months of imaging.

Biopsies to obtain specimens for research must be determined to be minimal risk prior to performance. Tumor tissue specimens are to be obtained from the target lymph node metastases, with or without image guidance. Types of biopsies are to include: 3-4 (1-2 cm in length), 14-16 or 18-gauge core biopsies, or small incisional biopsies (tumor biopsy at least 4-5 mm in diameter) such that the smallest dimension of the residual tumor after initial biopsy would be at least 1 cm [minimal size of single tumor is at least 2 cm in smallest dimension]. It is suggested that core biopsies be submitted separately into individual tissue blocks.

NOTE: Reimbursement guidelines for research biopsies are outlined in [Appendix XI](#).

Forms and Reports:

The following items are to be included with the pathology materials:

- Institutional Diagnostic and Surgical Pathology Report
- ECOG-ACRIN Generic Specimen Submission Form (#2981v3) [if STS is unavailable]
- Sample Tracking System (STS) Shipping Manifest Form
- Immunological study reports, if available

Mail pathology materials to:

ECOG-ACRIN Central Biorepository and Pathology Facility
MD Anderson Cancer Center

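### Research biopsies of the target node after the RECIST baseline scan may be incisional, and no rule stops the removed tissue from contributing to a recorded partial response; the likely effect on RR is small

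*Combined protocol and SAP*

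**What the plan says.** **Order of events.** Section 3.1.3 requires measurable disease on imaging "obtained within 4 weeks prior to registration as defined by RECIST"; Section 7.1 repeats the timing. The research biopsies come later. The first is placed at "Baseline, following step 1 registration prior to treatment", and only if no tissue from the preceding two months is available. The second is at week 2, plus or minus one week.

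**What is sampled.** Section 10.1.3.2: "Tumor tissue specimens will be obtained from the target lymph node metastasis, with or without image guidance". Cores are one option. The other is "small incisional biopsies (tumor biopsy at least 4-5 mm in diameter) such that the smallest dimension of the residual tumor after initial biopsy" is no less than 1 cm. Appendix I repeats the rule and adds a condition missing from 10.1.3.2: "minimal size of single tumor is at least 2 cm in smallest dimension".

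**How response is read.** Section 6.1.3 measures nodes by short axis only, treats a node of 15 mm or more on CT as measurable, and takes up to two lesions per organ and five in total as targets. PR in 6.1.5.2 is "At least a 30% decrease in the sum of the diameters of target lesions, taking as reference the baseline sum diameters". Section 6.1.5.5 adds: "Best response will be collected at one time point", after 8 weeks. Nothing in Section 6 excludes, re-measures or flags a target node biopsied after the baseline scan.

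**Use of the result.** RR is a secondary endpoint with a 95% confidence interval (9.5), and Section 2.2.2 sets out to describe how pCR correlates with it.

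**The concern.** The reference measurement is taken before tissue is removed and the response measurement after. Any short-axis loss caused by the biopsy is then counted in the same way as shrinkage on drug. For RR the error runs towards more responses, and only in patients who consent to a biopsy and have it done by incision.

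The pCR-by-RR comparison is exposed as well. At the response rates cited in the background (63% and 86%), about 5 to 14 of 39 patients would be RECIST non-responders, so one recoded patient is a visible share of that group.

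The plan recognises this type of problem elsewhere. Section 9.7.2 places the baseline FLT-PET before the baseline biopsy to avoid confounding. That discussion covers only FLT-PET and only needle biopsies; RECIST has no counterpart.

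**Working it through.** The plan gives no figure for this effect, so there is none to reproduce. The check applies the plan's own limits to the PR rule.

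**Inputs from the documents:** measurable node 15 mm or more (6.1.3); PR at a fall of 30% or more (6.1.5.2); incisional piece at least 4-5 mm and residual at least 10 mm after the initial biopsy (10.1.3.2); tumour at least 20 mm (Appendix I only); 39 evaluable patients (9.1).

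**1. Does the 1 cm residual rule out PR?** A 10 mm residual is a fall of at least 30% when the baseline is at least 10 / 0.7 = 14.3 mm. That covers every CT-measurable node, so for a sole target node it does not. At the limit:
- 15 mm to 10 mm: 5/15 = 33.3% (possible under 10.1.3.2, excluded by Appendix I)
- 20 mm to 10 mm: 10/20 = 50%

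**2. What does a minimum biopsy do?** Percent fall = mm lost from the short axis / baseline sum. The table assumes the full 4-5 mm is lost along the measured axis.

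| Sole target node | One biopsy | Two biopsies |
|---|---|---|
| 20 mm | 20-25% | 40-50% |
| 25 mm | 16-20% | 32-40% |
| 30 mm | 13.3-16.7% | 26.7-33.3% |

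At 20 mm or more, one minimum biopsy stays below 30%. A 20 mm node needs a further true shrinkage of 5-10% of baseline to reach PR.

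**3. Is a loss of 4-5 mm realistic?** For a 20 mm sphere (radius R = 10), shortening one axis by h = 5 mm means removing a cap of width 2 x sqrt(2Rh - h^2) = 2 x sqrt(75) = 17.3 mm and volume share h^2(3R - h)/(4R^3) = 625/4000 = 15.6%. A 5 mm piece is about (5/20)^3 = 1.6% of the volume. Spread evenly, that changes the diameter by 1 - (1 - 0.0156)^(1/3) = 0.5%; a 4 mm piece changes it by 0.3%. The table is therefore an upper limit for a minimum-size biopsy.

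**4. More than one target.** With 20 + 20 mm and one node cut to 10 mm, the fall is 10/40 = 25%. With 20 + 15 mm and the 20 mm node cut to 10 mm, it is 10/35 = 28.6%. Neither reaches PR without true shrinkage.

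**5. Effect on RR.** One recoded patient is 1/39 = 2.6 points: for example, 25/39 = 64.1% (95% CI 47.2-78.8) becomes 26/39 = 66.7% (49.8-80.9).

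For a population figure, inflation = (1 - RR) x fraction with one incisional biopsy x probability of recoding. The response rates are from Sections 1.2 and 1.4: 63% for this combination in the phase 3 trial in advanced disease, and 86% in a neoadjuvant trial of another BRAF/MEK pair. Everything else is assumed: 25% of patients have one incisional biopsy; there is a single target node with median short axis 20-30 mm (log-SD 0.35); non-responders' true change is uniform from -29% to +19%; and the full 4-5 mm is lost along the axis. Simulation then puts recoding of non-responders after one biopsy at 23-36%.
- Low: 0.14 x 0.25 x 0.23 = 0.8 points
- High: 0.37 x 0.25 x 0.36 = 3.3 points
- With 10% incisional: 0.3 to 1.3 points

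Varying the node-size limit and the way loss and growth combine widens recoding to 20-46%, or 0.7 to 4.3 points at 25%. If the loss is not along the short axis, the effect is close to zero.

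**The case against.** A reader might infer that a biopsy alone routinely turns a non-responder into a PR, or that RR will be materially inflated. The documents do not support that.

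- The text describes small incisions. The 1 cm figure is a floor on what must remain, not a permission to cut down to it, and halving a 20 mm node is hardly small. This stands: the limiting cases show that nothing prevents the error, not that it is likely.
- Incisional sampling looks exceptional. Section 9.7.2 speaks of needle biopsies, and Appendix XI reimburses only CT- or ultrasound-guided node biopsies and ultrasound-guided skin biopsies. Cores should barely alter the short axis. This stands, and no document gives an incisional fraction.
- Two biopsies in one patient will be uncommon. The first is requested only without recent tissue, and Section 9.7.3.2 expects small numbers at week 2. This stands, so two-biopsy figures should not drive the estimate.
- Section 10.1.3.2 does not expressly say that its target node is the RECIST target. This carries less weight: a node of 2 cm is measurable and targets are chosen by size, so the two will usually coincide.

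A reader might also infer that biopsy hides progression: a 20 mm node cut to 15 mm that then grows 40% reads 21 mm, or +5%. The arithmetic is right, but the pooled analysis in Section 1.4 reports no progression before surgery on targeted therapy, so this is a remote case.

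**Conclusion.** The gap is real. Tissue removed from a target node between the baseline scan and week 8 is not distinguished from response, and the 1 cm residual does not exclude a 30% fall in a sole target node. PR after one minimum biopsy of a node of at least 2 cm still needs a larger cut, a second biopsy or some true shrinkage.

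The probable effect on RR is small. The 0.8 to 3.3 points rest on an assumed 25% with one incisional biopsy, a single target and full loss along the measured axis. That is well inside a confidence interval about 31 points wide. Core-only sampling or several targets shrink it further.

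Primary pCR and the two-stage decision rule do not use RECIST PR and are unaffected. A RECIST CR cannot come from the initial biopsy alone, because it needs a short axis below 10 mm. The case for acting is that the remedy is cheap, and that the effect cannot be separated later unless biopsy type is recorded.

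**What to change.** 1. **Section 6.1.3.** When an incisional baseline biopsy is planned and another measurable lesion exists, prefer the unsampled lesion as target. Do not change targets after baseline, so a week-2 biopsy is dealt with by item 2. The section already allows a smaller lesion to be chosen when the largest is unsuitable for repeat measurement.
2. **Biopsy form and Section 9.5.** Record biopsy type, lesion and date. Flag patients whose target node had an incisional biopsy between the baseline scan and the week-8 assessment, including week 2. Report RR and its association with pCR as planned, and again in a sensitivity analysis that either excludes flagged patients or counts their PRs as non-response. State in advance which.
3. **Section 10.1.3.2 and Appendix I.** Reconcile the two on minimum tumour size for biopsy. Which rule is right is for the study team to decide.

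The cost is one added entry on the biopsy form, one extra analysis, and the largest node sometimes not being a target. No extra scan, biopsy or patient is needed.

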10.1.4 Shipping Procedures

Tumor tissue specimens are to be shipped overnight at ambient temperature within one (1) month following registration or collection. During warm months, it is strongly recommended that tumor tissue specimens be shipped with a cool pack to prevent the paraffin from melting.

Ship using the CBPF's FedEx account using the FedEx on-line ship manager.

Ship to:

ECOG-ACRIN Central Biorepository and Pathology Facility
MD Anderson Cancer Center
Department of Pathology, Unit 085
Tissue Qualification Laboratory for ECOG-ACRIN, Room G1.3598
[name]
[name]
Phone: Toll Free [contact] [contact] Local or
International Sites)
[contact]
Email: [contact]

Access to the FedEx shipping account for shipments to the ECOG-ACRIN CBPF at MD Anderson Cancer Center can only be obtained by logging onto [fedex.com](#) with an account issued by the ECOG-ACRIN CBPF. For security reasons, the account number will no longer be given out in protocols, over the phone, or via email. If your site needs to have an account created, please contact the ECOG-ACRIN CBPF by email at [contact].

An STS Shipping Manifest Form must be generated and shipped with all specimen submissions.

10.2 Peripheral Blood Submissions:

10.2.1 Submissions to the MD Anderson Cancer Center CBPF Life Science Plaza

Submit from patients who answer 'Yes' to '*I agree to provide additional blood samples for future health research.*'

Kits for the collection and shipment of the peripheral blood specimens are ordered online from Cenetro Central Laboratories. Instructions are provided in [Appendix VIII](#). Questions regarding kits can be directed to [contact] or call the Cenetro Clinical Trials Group at [contact]. Kits must be ordered after the patient has been registered to the trial and will generally arrive within three (3) business days from when the order was placed.

10.2.2 Collection Schedule

Peripheral blood specimens are to be collected at the following time points:

- Prior to Start of Treatment
- After Two Weeks of Therapy
- After Eight Weeks of Therapy
- Weeks: 20, 32, 44, and End of Treatment

10.2.3 Sample Preparation Guidelines

Package and ship at ambient temperature. SST Red Top and Streck tubes may be packaged with cool packs during the hot season, but the Green Top Heparin tubes are to be shipped ambient only. If a cool pack is used, specimens must be packaged to protect them from freezing, otherwise just ship ambient.

1. Red Top SST Tubes

- Draw two (2) 10mL red top SST tubes of whole blood at each time point.

2. Green Top Heparin Tubes

- Draw ten (10) 10mL green top heparin tubes of whole blood at each time point.

3. Streck Cell-Free DNA Tubes

- Draw one (1) 10mL Streck Cell-Free DNA BCT tube of whole blood at each time point. Fill each tube completely.
- Ensure at least 10mL of blood is drawn in each tube. Avoid low volume to minimize agitation during shipping.
- Immediately after collection, gently invert tube 180 degrees and back 10 times to ensure adequate mixing.
- Maintain blood at room temperature (6°C to 37°C) until shipping. **Do Not** place tube in refrigerator.

